2.3 REGISTRATION PROCEDURES

Registration and status updates (e.g., when a participant is taken off protocol therapy and when a participant is taken off-study) will take place per CCR SOP ADCR-2, CCR Participant Registration & Status Updates found at: [https://nih.sharepoint.com/sites/NCI-CCR-OCD-Communications/SitePages/OEC-Administrative---Clinical-Research-\(ADCR\).aspx?Mode=Edit](https://nih.sharepoint.com/sites/NCI-CCR-OCD-Communications/SitePages/OEC-Administrative---Clinical-Research-(ADCR).aspx?Mode=Edit)

2.3.1 Screen Failures

Screen failures are defined as participants who consent to participate in the clinical trial but are not subsequently assigned to the study intervention or entered in the study. A minimal set of screen failure information is required to ensure transparent reporting of screen failure participants, to meet the Consolidated Standards of Reporting Trials (CONSORT) publishing requirements and to respond to queries from regulatory authorities. Minimal information includes demography, screen failure details, eligibility criteria, and any serious adverse event (SAE).

Individuals who do not meet the criteria for participation in this trial (screen failure) may be rescreened at the discretion of the PI. Rescreened participants should be assigned a different participant number as for the initial screening.

2.4 TREATMENT ASSIGNMENT AND RANDOMIZATION/STRATIFICATION PROCEDURES

Cohorts

Number	Name	Description
ES1	Phase I, Dose Escalation Cohort 1	Patients with epithelial ovarian cancer, primary peritoneal cancer or fallopian tube cancer that is relapsed and platinum resistant or refractory
EX1	Dose Expansion Cohort 1	10 additional patients will be treated at the MTD

Arms

Number	Name	Description

Abbreviated Title: Phase 1 IFN + monocytes

Version Date: 12/04/2025

ES1	Phase 1, Dose Escalation Arm	The autologous monocytes cell product in 250ml total volume of investigational combination (monocytes + ACTIMMUNE + SYLATRON) is infused via the intraperitoneal catheter or port over 30-60 min +/- 10 min every 28 days +/- 7 days until disease progression, limiting toxicity, intercurrent medical issues, or patient withdrawal.
EX1	Dose Expansion Arm	10 additional patients will be treated at the MTD, defined as Dose Level 4: autologous monocytes cell product in 250ml total volume of investigational combination: Monocytes (750 x 10⁶ ± 20%) + ACTIMMUNE 50 mcg (0.2 µg/mL) + SYLATRON 250 mcg (1 µg/mL) is infused via the intraperitoneal catheter or port over 30-60 min +/- 10 min every 28 days +/- 7 days until disease progression, limiting toxicity, intercurrent medical issues, or patient withdrawal.

Randomization and Arm Assignment

Randomization and stratification procedures do not apply to this trial.

Patients in Cohort ES1 will be directly assigned to Arm ES1.

Patients in Cohort EX1 will be directly assigned to Arm EX1.

2.5 BASELINE EVALUATION

Scans and x-rays must be done within 28 days (- 7 days) prior to the initiation of study therapy. All other studies should be performed within 7 days prior to initiation of study therapy, unless otherwise specified. If the activities performed during Screening Part 2 fall within these designated timeframes, they will not need to be repeated at baseline.

Baseline Assessments	Timeframe (calendar days)
	Within 7 days prior to treatment (unless otherwise noted)
History and physical examination	X
Assessment of disease by imaging (may include CT chest, abdomen and pelvis)	Within 28 days prior to treatment
Assessment of venous access in Department of Transfusion Medicine	Anytime prior to apheresis
CBC with differential and platelet count	X
Metabolic panel (magnesium, calcium, albumin, phosphorus)	X

Baseline Assessments	Timeframe (calendar days)
	Within 7 days prior to treatment (unless otherwise noted)
Acute care panel (electrolytes, glucose, BUN, creatinine)	X
Hepatic function tests (AST/ALT/total bilirubin)	X
CA125	X
β -HCG in women of childbearing potential	X

3 STUDY IMPLEMENTATION

3.1 STUDY DESIGN

This is a single arm dose escalation study including an expansion cohort at the MTD.

A 3+3 phase I trial of monocytes with Sylatron® (Peginterferon alfa-2b) and Actimmune® (Interferon gamma-1b) dose escalation will proceed to determine the MTD. The dose-limiting toxicity (DLT) period will be during the first cycle (28 days). For each dose level, three patients will be enrolled. There will be a 2 week wait from the time of cell infusion from one patient until apheresis and cell infusion of the next patient. If any patient assigned to a particular dose level experiences DLT, then up to three additional patients (up to a total of six patients) will be enrolled at that dose level. All patients on a dose-level must complete the 28-day cycle prior to beginning enrollment on the next dose level. If any patient experiences DLT-like adverse events related to experimental agents or study procedures in subsequent cycles, enrollment will be placed on hold until evaluated by the IRB and FDA.

Following Registration Part 2, patients will have intravenous access assessment in the Department of Transfusion Medicine (DTM) Dowling Clinic and a tunneled IP catheter will be placed in interventional radiology (IR) using ultrasound guidance. The tunneled IP catheter will be placed prior to start of the protocol therapy. If the patient already has an existing IP port for prior IP chemotherapy, this can be used for IP infusion, and a new tunneled catheter will not be placed. The patient will also be given the option to have an IP port placed instead of a tunneled catheter. If she prefers the IP port, she will be evaluated and if the procedure is deemed safe and feasible, it will be performed using direct visualization in the operating room (laparoscopic camera). Research blood will be collected, and ascites will be collected if present. In the expansion cohort, solid tumor will be biopsied if amenable at the time of catheter or port placement. The purpose of the biopsy is to assess monocyte and other immune cell infiltration and differentiation related to treatment.

On Day 0, the patient will undergo intravenous line placement and apheresis in DTM. PBMCs will be stored according to standard operating procedures of DTM ([Appendix B](#)). For patients on DL1 and DL3b, there will be no Day 0 in the calendar as they will not be apheresed.

On Day 1, monocytes will be elutriated, quantified, and mixed with interferons. The final product will be infused in the inpatient setting through the IP catheter/port, as per standard operating procedure described in [Appendix D](#). Patient will be observed overnight for adverse events.

Patient will be discharged on Day 2, if well, with IV lines removed. IP catheter can be left in place or removed at physician discretion. Cycle will be repeated every 28 days. A new product will be manufactured for each treatment cycle.

In the expansion cohort, solid tumor will be biopsied again, if amenable, on C2D1 and at the time of disease progression. The purpose of these biopsies is to assess monocyte and other immune cell infiltration and differentiation related to treatment.

After 2 cycles, the patient may be treated as an outpatient per physician discretion.

Imaging will be performed at baseline and every 2 cycles.

3.1.1 Dose Limiting Toxicity

Dose-limiting toxicity (DLT) evaluation period is the first cycle. DLT is defined as:

- \geq Grade 3 fatigue (defined as fatigue not relieved by rest, limiting self-care ADLs) lasting > 7 days
- \geq Grade 3 cytopenias lasting > 7 days
- \geq Grade 3 transaminitis lasting > 7 days
- \geq Grade 3 depression lasting > 7 days
- \geq Grade 3 abdominal pain lasting > 7 days
- Any other grade ≥ 3 toxicity lasting > 72 hours despite maximal medical intervention

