3.2 DRUG ADMINISTRATION

Monocytes are collected, elutriated and mixed with interferons according to [Appendix B](#).

The cell product is delivered to the inpatient ward, and infused within 4 hours after preparation. The cell product in 250 mL is infused via the intraperitoneal catheter/port over 30-60 min +/- 10 min.

After 2 cycles, per physician discretion, the infusion can be given as an outpatient in the day hospital/infusion center.

The administration is repeated every 28 days +/- 7 days to accommodate for holidays, inclement weather, or other scheduling conflicts.

Interactions between interferon gamma-1b and other drugs have not been fully evaluated. Caution should be exercised when administering interferon gamma-1b in combination with other potentially myelosuppressive agent. Preclinical studies in rodents using species-specific interferon-gamma have demonstrated a decrease in hepatic microsomal cytochrome P-450 concentrations. This could potentially lead to a depression of the hepatic metabolism of certain drugs that utilize this degradative pathway.

Peginterferon alfa-2b inhibits CYP1A2 and CYP2D6 activity. Monitor for potential increased toxicities of drugs metabolized by CYP1A2 and/or CYP2D6 with a low therapeutic index or a narrow therapeutic range when they are administered concomitantly with peginterferon alfa-2b.

Patients will continue therapy until documentation of progressive disease, limiting toxicity, intercurrent medical issues, or patient withdrawal

Participants will be contacted remotely or assessed in person at least once weekly during the first cycle of treatment. Subsequent follow up will be at least monthly, with the start of each new cycle, and then during follow up according to the defined schedule (see Study Calendar, Section [3.4](#)).

Pre-cycle and off-treatment AE assessments will be done at a scheduled clinic visit. Post-therapy follow-up assessments will be performed within 30 days of stopping study treatment over the phone or at a clinic visit.

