3.4 STUDY CALENDAR

Baseline evaluations are to be conducted within 7 days prior to start of protocol therapy, unless otherwise specified. Scans and x-rays must be done within 28 days (- 7 days) prior to the start of therapy. In the event that the patient's condition is deteriorating, laboratory evaluations should be repeated within 48 hours prior to initiation of the next cycle of therapy.

1 cycle = 28 days

Procedure	Screening/ Baseline ^{15, 17}	Cycle 1 ¹						Cycle 2		Subsequent cycles	Post Therapy Follow- up ²
		Day -2 or -1	Day 0 ⁵	Day 1 ¹⁴	Day 2 ¹²	Day 27 ⁴		Day 1	Day 2 ¹²		
Clinical Assessment	X									X	X
Physical Exam		X		X	X	X		X	X	X	X
Vital signs	X	X	X	X	X	X		X	X	X	X
Performance Score	X	X				X				X	X
Offer NIH Advanced Directives Form ¹⁰	X										
Ophthalmic evaluation ⁶	X										
Tunneled IP catheter or IP port placement ⁷	X										
Venous access assessment	X										
Establish venous access prior to each apheresis			X							X	
Apheresis ¹³			X							X	
Autologous monocytes mixed with Sylatron® (Interferon Alfa-2b) and Actimmune® (Interferon Gamma-1b), IP infusion				X				X		X	
Labs (See Section 2.2 and 2.5) ¹¹	X	X		X	X	X		X	X	X	X

Procedure	Screening/ Baseline ^{15, 17}	Cycle 1 ¹						Cycle 2		Subsequent cycles	Post Therapy Follow- up ²
		Day -2 or -1	Day 0 ⁵	Day 1 ¹⁴	Day 2 ¹²	Day 27 ⁴		Day 1	Day 2 ¹²		
Research blood collection ⁸		X			X	X ³			X	X ³	
Ascites collection ⁸		X				X ³					
Biopsy (expansion) ⁸		X				X		X			X
Radiological Assessments (may include CT-C/A/P or MRI; report from outside institution is acceptable) ¹⁶	X										
Restaging imaging ⁹			Every 2 cycles							X	
Adverse Events		X	→							X	
Concomitant Medications		X	→							X	

¹Weekly phone calls will be made during cycle 1.

²Post therapy follow up will be at one month following the last dose of treatment; however, AEs due to toxicity or research will be followed until resolution to \leq grade 1. If the patient cannot return to the Clinical Center for this visit, a request will be made to collect required clinical labs (specify as needed) from a local physician or laboratory. If this is not possible, patients may be assessed by telephone for symptoms. If patient has begun another treatment regimen or palliative care, follow up may be done by telephone, and exam/labs will be omitted.

³Must be done prior to administration of study agents.

⁴Flexibility +/- 7 days permitted for Days 27-28 of each cycle.

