⁵ Day 0 procedures do not apply for patients in the Dose Level 1 or Dose Level 3b cohort ⁶Ophthalmic evaluation including visual acuity and funduscopy by an ophthalmologist within 180 days (-14 days) prior to treatment.

⁷ IP catheter or port can be placed at any time prior to the start of protocol therapy. If patient has pre-existing IP catheter or IP port, this will be assessed by the clinician for determination of function within the same time frame as other baseline studies. See Section 3.1 for additional information.

⁸ Research blood, ascites and biopsy testing will be performed in the NIH laboratory, [name]. [contact].

⁹ Restaging should be performed within +/- 7 days of completion of previous cycle.

¹⁰ As indicated in section 12.3, all subjects \geq age 18 will be offered the opportunity to complete an NIH advanced directives form. This should be done preferably at baseline but can be done at any time during the study as long as the capacity to do so is retained. The completion of the form is strongly recommended, but is not required.

¹¹ CA125 lab will be drawn at the beginning of each cycle. Day 2 labs will include only CBC with differential and platelet count, unless other labs are clinically indicated.

¹² Day 2 activities apply to the first two cycles only.

¹³ Apheresis collection will be done every 1-3 months provided there is an adequate monocyte population at the time of apheresis collection. If the apheresis collection is inadequate, apheresis can be done as frequently as each cycle to obtain the desired number of monocytes.

¹⁴ Do not repeat labs if already done within 1 week.

¹⁵ Performance score (ECOG) will be performed at the beginning of each cycle.

¹⁶ MRI is performed only as clinically indicated if patient cannot tolerate CT scan with IV contrast.

¹⁷ Screening and Baseline activities will be performed according to Sections [2.2](#) and [2.5](#) respectively.

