3.5.1 Criteria for removal from protocol therapy

- Progressive disease
- Participant requests to be withdrawn from active therapy
- Unacceptable Toxicity as defined in Section [3.1](#)
- Investigator discretion
- Positive pregnancy test
- Procedure failure (incapacity to do apheresis or obtain intraperitoneal access)
- Lost to follow-up
- Intercurrent illness

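### Two laboratory DLTs must last more than 7 days, but cycle 1 schedules no blood test between Day 2 and the Day 27 visit, so a silent episode can go uncounted

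*Combined protocol and SAP*

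**What the plan says.** Section 3.1.1 lists six DLT criteria. Two are read from blood tests, and each needs grade 3 or higher for more than 7 days: cytopenias, and "Grade 3 transaminitis lasting > 7 days". Section 3.1 sets the observation window: "The dose-limiting toxicity (DLT) period will be during the first cycle (28 days").

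In the 3.4 calendar, the row "Labs (See Section 2.2 and 2.5") is marked in cycle 1 on Day -2 or -1, Day 1, Day 2 and Day 27. Three footnotes qualify it:

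- Footnote 11: "Day 2 labs will include only CBC with differential and platelet count, unless other labs are clinically indicated".
- Footnote 14, attached to Day 1: "Do not repeat labs if already done within 1 week".
- Footnote 4 allows 7 days either side for Days 27-28.

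Between Day 2 and Day 27 the plan provides contact only. Footnote 1 describes weekly phone calls, and 3.2 says "Participants will be contacted remotely or assessed in person at least once weekly during the first cycle of treatment". Neither attaches a blood test.

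**The concern.** The plan defines two DLTs by a laboratory grade and a duration, but does not schedule the tests needed to observe either during most of the DLT period. These are also expected toxicities. Section 14.1 lists raised AST and ALT among the most common labelled reactions to subcutaneous peginterferon alfa-2b. Section 14.2 lists AST/ALT elevation, neutropenia and thrombocytopenia for interferon gamma-1b.

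Two things are at stake. Any expansion patient still to be treated at Dose Level 4 has a planned gap in cycle 1 safety monitoring. And 3.1.2 pools the 10 expansion patients with those already treated at the MTD (16 in all, per section 10) to sharpen the safety and toxicity estimates. In that pooled summary, a reader cannot tell a patient without a laboratory DLT from a patient who was not tested.

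**Working it through.** The plan states no figure on this point, so there is none to reproduce. The check is a count of days.

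**Inputs.** Last scheduled CBC before the gap: Day 2 (3.4, footnote 11). Last scheduled AST/ALT: Day 1, or earlier if footnote 14 applies. Next scheduled test: Day 27, movable to 27 - 7 = 20 or 27 + 7 = 34 (footnote 4). Shortest qualifying episode in whole days: 8.

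**Step 1, length of the gap** = visit day minus last test day.

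| Visit | CBC | AST/ALT (at least) |
|---|---|---|
| Day 20 | 20 - 2 = 18 | 20 - 1 = 19 |
| Day 27 | 27 - 2 = 25 | 27 - 1 = 26 |
| Day 34 | 34 - 2 = 32 | 34 - 1 = 33 |

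A visit on Day 34 also lies beyond the 28-day DLT period.

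**Step 2, does a qualifying episode fit?** The untested days number one fewer than the gap. An 8-day episode has (untested days - 8 + 1) possible start days on which it is wholly unseen.

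- Visit on Day 20: CBC 17 - 7 = 10 start days; AST/ALT 18 - 7 = 11.
- Visit on Day 27: CBC 24 - 7 = 17; AST/ALT 25 - 7 = 18.

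So it fits even in the shortest gap.

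**Step 3, does anything else in the plan supply a test?** Weekly contact can prompt a test, but only if there is something to report. The calendar's instruction to repeat laboratory work in a deteriorating patient concerns the 48 hours before the next cycle. After the infusion, research blood in cycle 1 falls only on Day 2 and Day 27. The follow-up duties in 6.1 and 8.2 start once an event is recognised. None of these provides a mid-cycle test in a patient who feels well.

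**Step 4, what would close it?** Any 8 consecutive days within Days 1 to 28 include Day 8, 15 or 22: starts on Days 1-8 include Day 8, starts on Days 9-15 include Day 15, and starts on Days 16-21 include Day 22. Weekly draws therefore see every such episode at least once.

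Seeing it is not the same as showing that it lasted more than 7 days. Suppose duration is dated from first detection, and detection falls evenly over the 7 days after onset (an assumption). The share of episodes of D days then shown to exceed 7 days is (D - 7)/7: 1/7 = 14% for 8 days and 3/7 = 43% for 10 days. Extra draws need repeat testing and a stated dating rule to be useful.

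**The case against.** The strongest reply is that little depends on this now. Section 3.1.3 closes escalation with the MTD at Dose Level 4. The expansion amendment dates from February 2020, this version is dated December 2025, and the documents do not say that anyone remains to be treated. Section 10 commits to no DLT-rate estimate. There is one infusion per cycle, so no dose could be withheld in mid-cycle, and laboratory tests recur before each re-dosing. Section 3.1 also holds enrollment if related DLT-like events occur in later cycles. All of this stands and limits the consequence, but the enrollment hold does not fill the cycle 1 gap.

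A reader might infer that laboratory DLTs first found at the Day 27 visit are lost too. The documents do not support that. Section 6.1 requires follow-up to baseline or stabilization, 8.2 through resolution, and footnote 2 adds that "AEs due to toxicity or research will be followed until resolution to" grade 1 or lower. Persistence after detection can therefore be shown; only the onset is uncertain, because 3.1.1 has no dating rule. A cytopenia already present on Day 2 is also seen on schedule.

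Nor does 6.1 lose confirmed DLTs. Section 3.5.1 lists "Unacceptable Toxicity as defined in Section" 3.1 as a reason to stop therapy, so a confirmed event would normally meet a 6.1 recording trigger. Section 6.1 limits what is entered as an adverse event; it does not say that values go uncollected. What it leaves out is a grade 3 or higher value of unknown duration that is asymptomatic, untreated and not judged clinically significant.

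Finally, the sixth criterion in 3.1.1 (other grade 3 or higher toxicity beyond 72 hours) can also include laboratory findings. Weekly CBC and hepatic panels do not address it.

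**Conclusion.** The point holds as a limited design weakness. The plan as written can miss a silent grade 3 or higher cytopenia or transaminase rise that meets its own DLT definition. The scheduled gap is 25 days for the CBC (18 to 32) and at least 26 days for AST/ALT (19 to 33).

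The direction is under-counting. The size cannot be determined: the documents give no onset times, episode durations, DLT rate, laboratory share of DLTs or frequency of unscheduled testing.

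A reader might infer that Dose Level 4 was declared the MTD because laboratory DLTs were missed. The documents do not support that either. Nothing shows that any were missed, unscheduled tests may have been done, and any probability attached to the closed decision would rest on invented rates.

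The consequence is confined to cycle 1 monitoring of expansion patients still to be treated, if there are any, and to how the pooled safety estimate in 3.1.2 is read. The conclusion assumes only that the calendar and its footnotes are the complete testing schedule. It is worth fixing because the remedy is cheap.

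**What to change.** 1. **For any patient still to be treated**, add a CBC and hepatic panel to the weekly cycle 1 contacts at about Days 8, 15 and 22, plus Day 29 if the Day 27 visit falls later than that. A local laboratory is acceptable. After any grade 3 or higher value, repeat within 2-3 days and again by day 8 after first detection. State in 3.1.1 that duration runs from the first grade 3 or higher value, with a sensitivity count that runs from the day after the last value below grade 3.
2. **Amend 6.1** so that any laboratory value reaching a 3.1.1 grade is recorded as an adverse event regardless of symptoms.
3. **For patients already treated at the MTD**, report how many had a CBC or AST/ALT between Day 2 and the Day 27 visit. Give a sensitivity DLT count in which a grade 3 or higher value of unknown duration counts as a DLT.

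If no patient remains to be treated, only items 2 and 3 apply. The cost is three or four routine draws per remaining patient, repeat draws only after a grade 3 or higher value, some extra reporting, and a DLT count that may rise.

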3.1.2 Dose Escalation

Patients who do not complete treatment in cycle 1 for reasons other than study drug-related toxicity will be replaced. If 1 of 3 patients experiences DLT, the dose level will be expanded to 6 patients. If 2 patients in a dose level of 3 to 6 patients experience DLT, then the MTD will have been exceeded and the next lower dose level will be expanded to 6 patients. MTD will be the highest dose at which 0-1 of 6 patients experience DLT. If the planned highest dose level is reached and determined to be safe after expansion to 6 patients, it will be considered the MTD. An expansion cohort of 10 additional patients will be treated at the MTD and the results combined with those of patients at the MTD to obtain improved estimates of safety and toxicity as well as to perform analyses to address secondary objectives. If either dose level 3 or dose level 4 exceeds the MTD (≥ 2 patients on either dose level experience a DLT) then we will enroll 3-6 patients on dose level 3b.

Total Volume (250 mL)

Dose Level	Monocytes total number	SYLATRON ® Peginterferon alfa2b, mcg (final concentration)	ACTIMMUNE ® Interferon gamma-1b, mcg (final concentration)
1	0	25 mcg (0.1 μ g/mL)	5 mcg (0.02 μ g/mL)

2	$75 \times 10^6 \pm 20\%$	25 mcg (0.1 $\mu\text{g}/\text{mL}$)	5 mcg (0.02 $\mu\text{g}/\text{mL}$)
3	$750 \times 10^6 \pm 20\%$	25 mcg (0.1 $\mu\text{g}/\text{mL}$)	5 mcg (0.02 $\mu\text{g}/\text{mL}$)
3b*	0	250 mcg (1 $\mu\text{g}/\text{mL}$)	50 mcg (0.2 $\mu\text{g}/\text{mL}$)
4	$750 \times 10^6 \pm 20\%$	250 mcg (1 $\mu\text{g}/\text{mL}$)	50 mcg (0.2 $\mu\text{g}/\text{mL}$)

*DL3b will enroll if ≥ 2 subjects enrolled on DL3 or DL4 experience DLT

Number of Patients with DLT at a Given Dose Level	Escalation Decision Rule
0 out of 3	Enter up to 3 patients at the next dose level
≥ 2	Dose escalation will be stopped. This dose level will be declared the maximally administered dose (highest dose administered). Up to three (3) additional patients will be entered at the next lowest dose level if only 3 patients were treated previously at that dose.
1 out of 3	Enter up to 3 more patients at this dose level. 
• If 0 of these 3 patients experience DLT, proceed to the next dose level.• If 1 or more of this group suffer DLT, then dose escalation is stopped, and this dose is declared the maximally administered dose. UP to three (3) additional patients will be entered at the next lowest dose level if only 3 patients were treated previously at that dose.
≤ 1 out of 6 at highest dose level below the maximally administered dose	This is the MTD and is generally the recommended phase 2 dose. At least 6 patients must be entered at the recommended phase 2 dose.

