3.1.3 Maximum Tolerated Dose (MTD)

The Dose Escalation Phase has concluded, and the MTD is defined as Dose Level 4 (Amendment I, version date 02/11/2020).

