10 STATISTICAL CONSIDERATIONS

Patients will be accrued in standard 3+3 dose escalation design, with expansion to 6 patients at the MTD and 10 additional patients at the MTD to allow for sufficient patients to perform correlative studies.

The 16 patients treated at the MTD (6 from dose escalation /MTD determination plus 10 additional patients) will be used to evaluate biologic correlates. With 16 patients, there would be 80% power to detect a change (either actual change or fold/relative change as appropriate) in the number of activated monocytes from baseline to after one cycle of treatment which would be equal to $\frac{3}{4}$ of a standard deviation of the difference measured (effect size 0.75) with a two-tailed 0.05 significance level paired t-test. If there are usable paired results from 10 patients instead of 16, this would result in the ability to detect a change with a 1.0 effect size based on the same parameters. In addition, a large number of other parameters will be obtained via flow cytometry and the changes from baseline to after one cycle of therapy will be determined. Given the large number of possible tests performed and the exploratory nature of the evaluation, there will not be any formal adjustment for multiple comparisons for these parameters. However, with 16 patients, there would be 80% power for any of the tests comparing baseline to post-treatment to detect a one SD difference between the two time points (effect size 1.0) with a two-tailed 0.01 significance level paired t-test; if there are 10 patients, there would be 80% power to detect a 1.0 effect size with a two-tailed 0.05 significance level paired t-test. The results of these exploratory tests will be reported in the context of the number of such tests performed.

The clinical response rate (in patients with measurable disease) and time to progression (in all patients) will also be estimated in a preliminary fashion. Appropriate confidence intervals will be provided along with fractions responding and a Kaplan-Meier curve of TTP.

It is estimated that up to 24 patients will be required to complete all 4 dose levels plus 10 additional patients will be needed at the MTD. Thus up to 34 evaluable patients may be required.

In order to allow for a small number of invaluable patients, the accrual ceiling will be set at 40 patients. Expected accrual rate is 1-2 patients per month. The DLT period is one cycle.

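### A plain pooled DLT rate over the 16 MTD patients would be biased modestly downward, so the 10 expansion patients should also be reported alone

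*Combined protocol and SAP*

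**What the plan says.** Section 3.1.2 (Dose Escalation) sets the selection rule: "MTD will be the highest dose at which 0-1 of 6 patients experience DLT". For the top planned level it adds: "If the planned highest dose level is reached and determined to be safe after expansion to 6 patients, it will be considered the MTD". It then provides for the expansion: "An expansion cohort of 10 additional patients will be treated at the MTD", with "results combined with those of patients at the MTD to obtain improved estimates of safety and toxicity".

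Section 3.1.1 fixes the window: "Dose-limiting toxicity (DLT) evaluation period is the first cycle". Section 3.1.3 reports that selection has already taken place: "The Dose Escalation Phase has concluded, and the MTD is defined as Dose Level 4", which is the highest planned level.

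Section 10 confirms the 6 + 10 structure: "The 16 patients treated at the MTD (6 from dose escalation /MTD determination plus 10 additional patients"). It uses those 16 for biologic correlates. It promises confidence intervals for response rate and time to progression, but gives no estimator, interval or selection caveat for toxicity. Section 2.4 already holds escalation (ES1) and expansion (EX1) as separate cohorts and arms. No section says that toxicity will be reported for EX1 on its own.

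**The concern.** The six escalation patients at the MTD are in the pool because their dose passed a test on their own DLT count. Had two or more of them had a DLT, the dose would have been rejected and they would not be MTD patients. A simple proportion over all 16 treats them as an unselected sample. The ten expansion patients were not chosen through their outcomes, so their rate carries no such bias.

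What is at stake is the description of toxicity at the dose that the section 3.1.2 decision table calls generally the recommended phase 2 dose. The shortfall grows with the true rate, so the pooled figure flatters a dose most when its true DLT rate is high.

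**Working it through.** **The plan's own figures.** The documents state no DLT rate and no precision for one, so there is no toxicity figure to reproduce. The figure attached to the same 16 patients does reproduce: "With 16 patients, there would be 80% power to detect a change" of 0.75 SD with a two-sided 0.05 paired t-test gives 80.1% by the noncentral t distribution. So 6 + 10 = 16 is the intended MTD sample.

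**Inputs.** Six escalation patients, kept if at most 1 has a DLT (3.1.2); ten expansion patients (3.1.2, section 10); DLT counted in cycle 1 (3.1.1). The true DLT probability *p* is not given, so I let it range from 5% to 40%.

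**Selection.** Let X ~ Bin(6, *p*) be DLTs in the first six and Y ~ Bin(10, *p*) those in the expansion. The 3+3 paths that keep a dose are 0 of 3 followed by 0 or 1 of 3, and 1 of 3 followed by 0 of 3. Together these are exactly X ≤ 1. Then, with q = 1 − *p*:

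- P(dose passes) = q⁶ + 6*p*q⁵
- E[X | X ≤ 1] = 6*p*q⁵ / (q⁶ + 6*p*q⁵) = 6*p*/(1 + 5*p*)
- Expected pooled rate = [6*p*/(1 + 5*p*) + 10*p*] / 16
- Bias = −30*p*² / [16(1 + 5*p*)], negative for every *p* > 0

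At *p* = 0.20: 6(0.20)/2 = 0.60 expected DLTs in the six, plus 2.00 in the ten, gives 2.60/16 = 16.3%. At *p* = 0.30: 1.8/2.5 = 0.72, plus 3.00, gives 3.72/16 = 23.3%.

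**Error.** The pooled mean squared error is bias² + [w(1 − w) + 10*p*q]/256, with w = 6*p*/(1 + 5*p*). For the ten alone it is *p*q/10. RMSE is the square root.

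**Interval.** The exact (Clopper-Pearson) 95% upper limits for 0, 1, 2 and 3 events in 16 are 20.6%, 30.2%, 38.3% and 45.6%. At *p* = 0.40 the pooled interval lies wholly below the truth when X + Y ≤ 2. Given selection, P(X = 0) = 0.2 and P(X = 1) = 0.8, so the chance is 0.2 × 0.167 + 0.8 × 0.046 = 7.1%. The nominal figure is 2.5%.

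| True rate (assumed) | P(dose passes) | Expected pooled rate | Bias (points) | RMSE pooled | RMSE 10 alone | Pooled CI wholly below truth |
|---|---|---|---|---|---|---|
| 5% | 97% | 4.6% | −0.4 | 0.051 | 0.069 | 0.0% |
| 10% | 89% | 8.8% | −1.3 | 0.068 | 0.095 | 0.0% |
| 20% | 66% | 16.3% | −3.8 | 0.093 | 0.126 | 0.0% |
| 25% | 53% | 19.8% | −5.2 | 0.104 | 0.137 | 1.9% |
| 30% | 42% | 23.3% | −6.8 | 0.116 | 0.145 | 0.8% |
| 1/3 | 35% | 25.5% | −7.8 | 0.125 | 0.149 | 3.9% |
| 40% | 23% | 30.0% | −10.0 | 0.141 | 0.155 | 7.1% |

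The miss rate does not rise steadily because the exact limits move in steps. For the ten expansion patients alone it is 0.6% at a true 40% (no DLT in ten: 0.6¹⁰).

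**The case against.** The strongest reply is that the plan never commits to this estimator. The sentence in 3.1.2 speaks of safety and toxicity. It names no DLT rate, no proportion over 16 and no interval, and it does not exclude separate reporting. That stands: the point concerns what a plain pooled DLT proportion would do, and the plan leaves that route open without comment.

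A second reply is that pooling does improve the estimate. This also stands. At a true 30% the RMSE is 0.116 pooled, against 0.195 for the first six alone and 0.145 for the ten alone. Pooling has the smaller RMSE at every rate in the table.

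Third, nothing is decided on the pooled rate. The primary objective is met by the 3+3 rule, escalation is closed, and no power or sample-size figure uses a pooled DLT rate. That is correct, and it keeps the severity low.

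A reader might infer more: that the pooled interval is generally unreliable, or that all grade 3 or higher toxicity is understated by the same amounts. The documents support neither. The low-side miss stays below 2.5% at every rate checked up to 30%. It exceeds 2.5% only at 1/3 and 40%, and a dose with a true rate of 40% passes the rule only 23% of the time. Selection acts directly only on cycle-1 DLTs. Shorter grade 3 events and later-cycle events are affected only through their correlation with DLT, which the documents do not give and which was not quantified.

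Separate cohorts in section 2.4 make an expansion-only figure easy to produce, but they do not promise it, so the gap remains.

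**Conclusion.** The point holds as a reporting gap of minor severity. A plain cycle-1 DLT proportion over the 16 MTD patients is biased downward by 1.3 points at a true 10%, 3.8 at 20%, 6.8 at 30% and 10.0 at 40%. At rates up to 20% the bias is well inside the sampling error. It becomes material only at rates of about 30% and above.

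This rests on four assumptions: that the pooled toxicity estimate includes a DLT rate; that the top level was judged safe by the same at-most-1-of-6 rule; that DLTs are recorded in EX1 by the same definition; and that all patients at the dose share one true rate. The observed DLT count at Dose Level 4 is not in the documents, so the realised bias is unknown. The calculation does not show that Dose Level 4 is too toxic or that pooling is a mistake.

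**What to change.** In sections 3.1.2 and 10, state that the cycle-1 DLT rate will be reported for the 10 expansion patients (EX1) alone with an exact 95% confidence interval, next to the pooled 16-patient rate. Label the pooled rate as conditional on the first six having passed the at-most-1-of-6 rule. Keep the pooled figure.

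The cost is a sentence in each section, one table row and a label. No patients, data or changes of conduct are needed. The downside is a wider interval for the expansion-only figure: in a hypothetical result of 1 of 6 plus 2 of 10, the pooled rate is 3/16 = 18.8% (exact CI 4.0% to 45.6%) and the expansion-only rate is 2/10 = 20.0% (2.5% to 55.6%). Showing both lets the reader see the less variable figure and the unselected one together.
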